Tipping point analyses will be considered for further evaluating sensitivity of the results with respect to missing data. In such an analysis, the distribution of missing data in the active treatment group would be shifted by varying amounts, until a point is found where the results of the analysis cross the threshold of statistical significance specified in section 6.2.2. The plausibility of a shift of the found size is then used to assess the robustness of results to unobserved differences due to missing data.

Subjects who discontinue study treatment but remain in the study can continue to contribute ALSFRS-R data, which will be included in the analyses where applicable. However, in time-to-

event analyses subjects will be censored from follow-up one day after study treatment discontinuation.

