7.5.2.3 Respiratory event and other time-to-event endpoints

A 'time to respiratory event' composite endpoint consists of the following events:

- A decrease of one or more points from baseline in any of the ALSFRS-R respiratory function subdomain scores (items 10–12).
- Starting non-invasive mask ventilation (NIV).
- Meeting 'protocolised' criteria for NIV: SVC (supine) $\leq 50\%$ predicted.
- Invasive mechanical ventilation by intubation.
- Invasive mechanical ventilation by tracheostomy.
- Death.

Time to respiratory event is reached whenever any of the criteria has first been met.

The following time-to-event secondary efficacy variables will be evaluated using Cox's proportional hazards regression:

1. Time to tracheostomy, continuous ventilator dependence, or death (TRCVDDTH)
2. Time to NIV or death (NIVDEATH)
3. Time to respiratory event (RESPEVNT)

Individual components of all the composite endpoints will be analysed in the same fashion:

1. Time to continuous ventilator dependence (ALSFRS-R item 12 ≤ 1 ; CVD)
2. Time to decline from baseline in any ALSFRS-R respiratory domain score (FRSBR1D)
3. Time to SVC (supine) $\leq 50\%$ of predicted (SVC50PP)
4. Time to non-invasive mask ventilation (NIV)
5. Time to intubation (INTUB)
6. Time to tracheostomy (TRACH)
7. Time to death (DEATH)

As will these additional endpoints derived from the SVC and ALSFRS-R values:

1. Time to decline from baseline SVC (supine) by $\geq 20\%$ (SVC20PD)
2. Time to decline from baseline ALSFRS-R total score by $\geq 20\%$ (FRS20PD)
3. Time to continuous use of NIV during the night (ALSFRS-R item 12 ≤ 2)

The data for the time-to-event variables will be stored in the ADTTE dataset with parameter names corresponding to those in parentheses above.

The analysis model will include an effect for treatment, and will be adjusted for randomization strata. Premature discontinuations will be treated as right-censored in the analyses. Censoring rules for different scenarios are described in **Error! Reference source not found..** For the purpose of determining the end date, survival and ventilation status are considered to be assessed daily; ALSFRS-R and SVC measurements are assessed only on study visits. For composite

endpoints, the date of last assessment is defined to be the latest date at which the endpoint can be fully assessed: that is, the earliest date in the set of latest assessments of each of its component endpoints.

Table 2. Censoring rules for time-to-event analyses.

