Scenario	Censored	End date
Event criteria fulfilled	No	Date of endpoint assessment
Event criteria fulfilled at baseline	Yes	Date of randomization
Event criteria never assessed	Yes	Date of randomization
Completed Week 48 without event	Yes	Date of last endpoint assessment
Discontinued study	Yes	Date of last endpoint assessment
Discontinued study treatment (1 day after*)	Yes	Date of last endpoint assessment
Died, when death not part of event criteria	Yes	Date of last endpoint assessment
Died, when death is part of event criteria	No	Date of death

*) to account for potential events following immediately after the study treatment discontinuation.

SAS code in the following fashion will be used to fit the statistical models:

```
proc phreg data = ADTTE;
  where ITTFL = "Y" and PARAMCD = "RESPEVNT";
  class TRTP(ref = "PLACEBO") STRATAR;
  model AVAL * CNSR(1) = TRTP STRATAR / ties = efron rl;
run;
```

For descriptive purposes, Kaplan-Meier survival curves will be plotted in addition to the statistical analysis results from the Cox models. Also, restricted mean survival time (RMST) will be described graphically at 14-day intervals from start of follow-up up to 48 weeks. These analyses are used to visually inspect the plausibility of the proportional hazards assumption.

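### The SAP's drug-stop censoring rule and its death row conflict with no stated precedence; applied together they can bias time to death, and no Cox sensitivity analysis counts events after drug stop

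*SAP*

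**What the plan says.** SAP 6.2.5 notes that subjects who stop drug but stay in the study "can continue to contribute ALSFRS-R data, which will be included in the analyses where applicable". It then makes an exception for time-to-event endpoints: "event analyses subjects will be censored from follow-up one day after study treatment discontinuation". Death is not exempted.

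Table 2 in SAP 7.5.2.3 has three rows that bear on this:

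- The row "Discontinued study treatment (1 day after" (a footnote mark follows) is censored, with the last endpoint assessment as end date. The footnote explains the extra day: "to account for potential events following immediately after the study treatment discontinuation".
- The row "Died, when death is part of event criteria" is not censored and ends at the date of death. It has no on-drug condition.
- The row for fulfilled event criteria is likewise not censored, again with no on-drug condition.

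For composites, 7.5.2.3 sets the last assessment at "the earliest date in the set of latest assessments of each of its component endpoints". An SVC visit can therefore fix the censoring date, whereas 6.2.5 names one day after the stop.

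Protocol 4.5 and 6.1.6 keep recording ALSFRS-R, ventilatory support and survival after drug stop, at visits that are encouraged, not required. Protocol 8.4.3 says that premature discontinuations are censored and leaves the details to the SAP. Time to respiratory event is second in the secondary testing hierarchy (SAP 6.2.3 and 7.5.2). Time to death and time to NIV or death are outside it and supportive.

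**The concern.** A subject who stops drug, remains in the study and later dies fits two rows of Table 2 that give opposite answers. Two programmers could build different datasets from the same text, and the choice might be made after unblinding.

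The more serious possibility is that both rows are applied literally. Follow-up after the stop would then depend on outcome: kept for those who die, discarded for those who live. That inflates the death rate in whichever arm stops more often, even if the drug does nothing.

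Separately, censoring at drug stop can be informative if sicker subjects stop. The plan has no Cox analysis that would show this, although most of the data needed are already being collected.

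**Working it through.** **Inputs.** From SAP section 5: 450 subjects at 2:1 (300/150), a 48-week levosimendan event rate of 73% with hazard ratio 0.70 for the composite, placebo 12-month mortality of 15%, and a 20% relative improvement in survival (read here as 12% mortality). The documents give no drug-stop rate, only a dropout allowance of about 20%, so all stopping rates below are assumptions. Hazards are constant and time is in units of 48 weeks.

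**The plan's own figures.** The implied placebo event rate is 1 − 0.27^(1/0.70) = 84.6%, so events = 300×0.73 + 150×0.846 = 346. The stated power of about 70% is not reproduced by the Schoenfeld formula: Φ(√(346×2/9)×|ln 0.70| − 1.96) = 88%, or 80% with 20% dropout (277 events). Nothing below depends on that. Expected deaths by Week 48 are 150×(1 − 0.85^(48/52)) + 300×(1 − 0.88^(48/52)) = 20.9 + 33.4 = 54.3.

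**Step 1: both rows applied to time to death, no true effect.** Death hazard in both arms is m = −ln(0.85)×48/52 = 0.150. Stop hazard is θ = −ln(1−p), unrelated to prognosis.

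- Deaths counted per subject: 1 − e^(−m) = 0.1393, whatever the stopping rate.
- Follow-up per subject: those who die contribute (1 − (1+m)e^(−m))/m = 0.0679. Survivors, cut at the stop, contribute e^(−m)×p/θ = 0.8607×p/θ.

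| p | p/θ | follow-up | rate |
|---|---|---|---|
| 10% | 0.949 | 0.885 | 0.157 |
| 15% | 0.923 | 0.862 | 0.162 |
| 25% | 0.869 | 0.816 | 0.171 |
| 30% | 0.841 | 0.792 | 0.176 |

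The true rate is 0.150 in every row. Rate ratios, levosimendan v placebo, are 0.1707/0.1574 = 1.08 for 25% v 10%, and 0.1616/0.1759 = 0.92 for 15% v 30%. Cox fits to large simulated samples give about 1.08 to 1.09 and 0.91. Under either single rule (on-drug deaths only, or all deaths with full follow-up) they give 0.99 to 1.00. With equal stopping the mixed rule also gives 1.00.

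**Step 2: the ranked composite.** First events after stop, per arm with hazard l, number n×[θ/(θ+l)×(1 − e^(−(θ+l))) − e^(−l)(1 − e^(−θ))]. At p = 20%:

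- levosimendan (l = 1.309, θ = 0.223): 300×(0.1142 − 0.0540) = 18.0
- placebo (l = 1.870): 150×(0.0935 − 0.0308) = 9.4

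The total is 27.4. At 10% and 30% it is 13.4 and 42.3. These are upper bounds, because after the stop supine SVC is scheduled only at the end-of-study visit. The share that are deaths (factor m/l per arm) is 1.2/2.4/3.7 of 346, or 2.2/4.6/7.1 if off-drug mortality doubles. So few events change status that the mixed rule leaves the composite's null hazard ratio at about 1.00.

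**Step 3: informative stopping and the composite.** In 48 simulated scenarios with no true effect (600 runs each; 77% event rate; frailty variance 0.5 to 2; unequal and prognosis-related stopping), drug-stop censoring gave mean hazard ratios of 0.96 to 1.05, against 0.99 to 1.01 counting all events. Rejection was 3.5–7.3% against 3.5–6.7%, with a simulation standard error of about 0.9 points.

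**Step 4: search for an analysis that counts off-drug events.** None of SAP 7.5.4.1 to 7.5.4.11 does. The post-NIV analysis removes data. Tipping-point analyses (6.2.5) are only to be considered and concern missing values. CAFS and the Kaplan-Meier survival curve in 7.9.1 are not cut at drug stop, but neither is a sensitivity analysis of the Cox endpoints.

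**The case against.** The best reply is that the plan can be read coherently. SAP 6.2.5 censors without exception, and the drug-stop row with its one-day footnote would have little purpose if the event rows overrode it. A reader might infer that the SAP says nothing about deaths after the stop; it does not support that, because 6.2.5 read alone censors them. What remains is a death row with no on-drug limit and no sentence saying which row governs.

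The two censoring dates also largely reconcile. Survival and ventilation are treated as assessed daily, so the dates separate only for visit-based components. There, the last-assessment date avoids crediting unassessed time as event-free. That stands, and it is a reason to keep the Table 2 date.

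Three stronger readings are tempting, and none is supported:

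- That the censoring breaches the protocol. Protocol 8.4.3 provides for it.
- That the mandatory drug stop at invasive ventilation hides composite events. Intubation and tracheostomy are themselves composite events ("Invasive mechanical ventilation by intubation" is listed), so that link reaches only supportive endpoints such as time to death and time to NIV or death.
- That the row "Event criteria fulfilled at baseline", which censors at randomisation, is a further bias. It is an explicit rule on a pre-randomisation value, so it can cost events but does not bias the comparison, and the documents do not say how many subjects it affects.

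Finally, time to respiratory event is on the multiple-imputation list in 6.2.5. How imputation combines with drug-stop censoring is not stated, so the plain Cox simulation above does not exactly mirror the planned primary analysis. That limitation stands.

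**Conclusion.** The point holds as an internal conflict plus a missing sensitivity analysis. The conflict matters mainly for time to death. Applied literally, the two rows shift the null hazard ratio by roughly 8 to 9% in either direction when stopping differs between arms by 15 percentage points, even if stopping is unrelated to prognosis. The direction depends on which arm stops more, and the rates are assumed.

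For the ranked composite the conflict is negligible. Informative stopping could distort it by a few percent in unknown direction, and no planned Cox analysis would reveal this. It would be wrong to infer that the second-ranked test is in serious doubt. The rule should nevertheless be settled before unblinding.

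**What to change.** 1. In Table 2, apply one rule to every subject within an analysis. For the prespecified on-drug analysis, state that the drug-stop row governs deaths and non-fatal events alike, so that only events up to one day after the stop count. Keep the last-assessment end date of Table 2 and 7.5.2.3, and reword 6.2.5 to match. Simply declaring that every death counts, while surviving stoppers stay censored at the stop, would build in the bias shown in step 1.

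2. Add to SAP 7.5.4 a sensitivity analysis of time to respiratory event, time to NIV or death, and time to death. Count all recorded events to Week 48 regardless of drug stop. Follow every stopper, dead or alive, to Week 48, study withdrawal or last contact. Adapt the composite end-date rule, because the scheduled off-drug SVC ends with the end-of-study visit.

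The cost is SAP text and programming on data already planned. The limitation is that visits after the stop are voluntary, so ascertainment will be incomplete, and later composite events will come from ALSFRS-R, ventilation and death only.

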6.2.6 Outliers

Detection of outliers will be done via visual inspection. If outliers are detected, a sensitivity analysis excluding the outliers may be performed to evaluate their impact to the results.

SVC efforts that are judged by a central analyst to be of unacceptable quality (BTRGRCD = “U”) will be treated as missing data in the primary analyses.

6.2.7 Baseline values

Planned Visit 1 pre-dose measurements will be used as baseline values for all variables. Should the baseline measurement be missing, the corresponding measurement from the Screening visit will be used as baseline instead, before any missing data imputation.

For 12-lead ECG measurements, which are repeated three times before dosing at Visit 1, the mean of all successful measurements will be used as the baseline value. The most severe interpretation of the baseline contributing measurements will be chosen as the baseline interpretation.

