6.1.1 Procedures during the screening period

A screening visit will take place 4-14 days before the first study treatment administration. A prospective subject will receive both written and verbal information about the study, and will have an opportunity to ask questions and sufficient time to decide whether or not to participate in the study. A signed and dated written IC will be obtained (a witness may sign the consent form to indicate that the subject has given verbal consent).

Re-screening (one occasion, unless otherwise authorised by the Medical Monitor) is allowed for example in case the patient has been taking prohibited treatment within 3 months before the screening visit or the sitting SVC is not within the inclusion criterion limits (60-90%).

The following procedures will be performed at the screening visit to ensure fulfilling the inclusion/exclusion criteria:

- Demographic data (birth year, age, sex, race, geographic region) and weight and height will be recorded. BMI will be derived from weight and height automatically in electronic case report form (eCRF).
- ALS history (date of diagnosis, ALS family history, site of onset [spinal/bulbar] and start date of ALS symptoms) will be recorded.
- HR and BP will be recorded in supine position.
- 12-lead ECG will be recorded in supine position.
- Physical examination will be performed.
- A blood sample for haematology, clinical chemistry and serology will be collected and a urine sample will be collected for urinalysis. A pregnancy test will be performed for females of childbearing potential.
- Ability to swallow capsules will be tested with a placebo capsule.
- SVC will be measured in the sitting and supine positions. Sitting SVC% will be assessed
 first and used for inclusion criterion. Thereafter, SVC supine will be assessed only to
 ensure successful assessment.
- Status for NIV support, invasive mechanical ventilation by intubation or tracheostomy and survival will be recorded.
- AEs will be inquired.
- Medical history, current medical conditions and concomitant treatments will be recorded.
- Suicidality will be assessed.

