5. DETERMINATION OF SAMPLE SIZE

Sample size estimation is based primarily on supine SVC results from the study 3119001 LEVALS (Table 1). LEVALS had placebo-controlled data only up to 2 weeks, and therefore extrapolation of the results was needed. The placebo effect from phase II tirasemtiv trial BENEFIT-ALS (Shefner JM et al., 2016) was also evaluated.

Assuming a difference of at least 3.6% in change from baseline supine SVC between treatment groups and a common standard deviation of 10%, 164 evaluable subjects per group in a 1:1 allocation ratio have 90% power to detect a statistically significant difference in a two-sided, 5% α -level, two group T-test. Using a 2:1 allocation ratio, randomisation of 450 subjects to the study (approximately 300 levosimendan and 150 placebo treated subjects) allows for a total dropout rate of approximately 20%.

Table 1. Mean (SD) change from baseline SVC (supine) %-predicted in LEVALS

Treatment	2 weeks	12 weeks
Levosimendan 1 mg x 2	+2.4 (8.3)	-4.9
Levosimendan 1 mg x 1	+0.8 (8.6)	
Placebo	-3.6 (9.4)	-17.7 ¹
Placebo (BENEFIT-ALS)	-1.4	-8.5

¹ Extrapolated from the data

SD = standard deviation

Based on the dexpramipexole phase III study EMPOWER (Cudkowicz ME et al., 2013), a 12 point reduction in total ALSFRS-R score and a 15% mortality rate at 12 months can be assumed

in placebo treated patients. Assuming a 10 point decline in ALSFRS-R, with a standard deviation of 8 points, and a 20% relative improvement in survival, 450 patients provide approximately 80% simulated power to detect a statistically significant difference using a joint rank test. With 450 subjects and assuming a 48-week levosimendan event rate of 73% and hazard ratio of 0.70, time to respiratory event has approximately 70% power to detect a statistically significant difference using a log-rank test.

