6.2.2 Significance level and confidence intervals

Two-sided tests with a significance level of 5% will be used throughout the analyses. Corresponding 95% confidence intervals will be calculated for model-based contrasts, comparing the active treatment to placebo, using model-based standard error estimates.

The study has interim analyses that allow early stopping for futility, but not for efficacy. Therefore, we do not make adjustments to the significance levels in the final analyses.

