6.2.5 Dropouts and missing data

If a subject's data for a given planned visit is missing due to the actual visit having occurred outside the specified visit interval, data from the actual visit will be used for imputing data for the planned visit, if the time difference between the planned and actual visit no more than twice the tolerance for that visit. Otherwise, data will be imputed following the process for other types of missing data. See Figure 1 in section 2 for the visit timings and tolerance intervals.

In the primary evaluation, the flowing efficacy analyses will be conducted with missing data imputed using multiple imputation:

1. Supine slow vital capacity (SVC) through 12 weeks
2. Combined assessment of function and survival (CAFS) through 48 weeks
3. Time to respiratory event
4. Clinical Global Impression (CGI) through 48 weeks
5. Supine Borg CR 10 scale at 12 weeks
6. Slope of change in the ALSFRS-R respiratory domain through 48 weeks

For each imputed endpoint, 10 independent imputed data sets will be generated using the fully conditional specification (FCS) method. Predictive mean meatching will be used to impute continuous variables, and logistic regression methods for classification variables, as appropriate.

The imputation models will include measurements of the endpoint being imputed from all planned visits at which it should be collected, from the baseline visit up to the week 48 visit. The measurements are used in a one-row-per-subject format, by which all other visits' data are used to impute missing data at all visits. Further, the imputation model will also include time-invariant variables used in the statistical models or potentially associated with the missing outcome: treatment group, randomisation strata (site of onset, edaravone use, and region; as collected on the CRFs), sex, age group (< 65, 65–74, ≥ 75), and riluzole use status.

SAS code in the following fashion will be used to perform the imputation process:

```
proc mi nimpute = 10 seed = 270815;  
  class ARM STRATAV SEX AGEGR1 RILUZUSE;  
  var ARM STRATAV SEX AGEGR1 RILUZUSE AVAL1-AVAL8;  
  fcs regpmm (/ k = 5) logistic;  
run;
```

To ensure reproducibility of the imputation results, the randomly chosen seed value of 270815 will be used for all imputation procedures.

Imputation will be done directly based on the collected values, and derived quantities used for the analyses, like e.g. change from baseline, will be calculated after the imputation process,

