Primary efficacy will be evaluated based on the fitted model, using contrasts to obtain an estimate of the difference between the treatment and placebo at the Week 12 visit (Visit 5). Statistical significance of the Week 12 treatment difference will be tested. All SVC measurements from planned study visits prior to the Week 12 visit will be included in the estimation of the model.

SAS code in the following fashion will be used to perform the computations:

```
proc mixed data = ADEFF order = data alpha = 0.05 covtest;
  where ITTFL = "Y" and PARAMCD = "SVCPPSUP" and
    AVISIT in ("Week 2", "Week 4", "Week 8", "Week 12");
  class TRTP(ref = "PLACEBO") AVISIT STRATAR USUBJID SITEID;

  model CHG = BASE STRATAR TRTP AVISIT TRTP * AVISIT / ddfm = KR;
  repeated AVISIT / subject = USUBJID type = UN R;
  random SITEID / type = VC;

  estimate "Treatment Difference at Week 12"
    TRTP 1 -1 TRTP * AVISIT 0 0 0 1 0 0 0 -1 / cl;
run;
```

In the primary analysis, missing data are imputed using multiple imputation. As a result, the analysis above is repeated for each of the imputed data sets with the use of a by-statement. The analysis results are then pooled for inference according to the methods described in 6.2.5.

In additional analyses, data from all planned visits through 48 weeks will be included in the MMRM, and the treatment effect will be estimated with contrasts at each study visit. Further, a random slope model will be fitted, with visits' actual study days replacing the visit factor.

Changes in SVC (supine) between the last measurement while on treatment and the post-treatment measurement from their End of Study visit will be described.

Subgroup analyses will be conducted by removing the randomization stratum effect from the primary analysis model, and including the subgroup term and its interaction with treatment.

Descriptive statistics of SVC (supine) will also be presented by visit, treatment group, and angle of measurement position. The angle is categorised into three groups: 1) completely flat (0 degrees); 2) slightly elevated (up to 15 degrees); 3) unable to perform supine (> 15 degrees). The effect of angle of measurement will also be explored in an additional analysis, where the angle will be included as a factor in the primary analysis MMRM.

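### The primary supine SVC model and its imputation model leave out the screening supine SVC, a modest loss of precision that one extra pre-treatment covariate could recover

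*SAP*

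**What the plan says.** Protocol 6.1.1 provides that at the screening visit, 4-14 days before first dose, "SVC will be measured in the sitting and supine positions". Protocol 6.2.1 repeats the supine test at Visit 1 before dosing, and inclusion criterion 7 requires an adequate supine test at both visits. The protocol gives the purpose of the screening test as checking that the subject can perform it.

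SAP 6.2.7 then sets the baseline: "Planned Visit 1 pre-dose measurements will be used as baseline values for all variables". The screening value replaces it only when the Visit 1 value is missing. SAP 7.2 also tabulates screening supine SVC as a baseline characteristic, so the value is in the analysis data.

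The primary model in SAP 7.5.1.1 is "model CHG = BASE STRATAR TRTP AVISIT TRTP * AVISIT / ddfm = KR", with one baseline term. The imputation code in SAP 6.2.5 reads "var ARM STRATAV SEX AGEGR1 RILUZUSE AVAL1-AVAL8". The accompanying text runs the series from the baseline visit to Week 48, so the eight columns match Visits 1 to 8 and screening is not among them. None of the sensitivity analyses in SAP 7.5.4 uses the screening value as a covariate.

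**The concern.** A baseline reading is the subject's true level plus session error. When it is the only baseline covariate, part of that error stays in the residual variance of the Week 12 contrast. A second reading taken before treatment can remove some of it. It cannot bias a randomised comparison, because neither reading can be affected by treatment.

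The plan already treats the screening reading as an acceptable substitute baseline, and for ECG it averages three pre-dose recordings. It gives no reason for not using the repeat reading on the primary endpoint. What is at stake is the width of the primary confidence interval and a small amount of power.

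**Working it through.** **1. The plan's own figure.** SAP section 5 states: "Assuming a difference of at least 3.6% in change from baseline supine SVC between treatment groups and a common standard deviation of 10" (percent), and "164 evaluable subjects per group in a 1:1 allocation ratio have 90% power". SAP 6.2.2 sets a two-sided 5% level. A noncentral t calculation gives 164 per group (power 0.9015), so the figure reproduces. "Using a 2:1 allocation ratio, randomisation of 450 subjects to the study" with about 20% dropout leaves 360 evaluable, or 240 and 120. With SD 10 the power is then 0.895.

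**2. What the documents say about session error.** There is no test-retest figure. The SD of change over 2 weeks in LEVALS was 8.3 (1 mg x 2), 8.6 (1 mg x 1) and 9.4 (placebo). A change contains two session errors plus true change, so SD of change / √2 is a ceiling on the session SD: 8.3/1.414 = 5.87, 8.6/1.414 = 6.08, 9.4/1.414 = 6.65.

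**3. Model.** Let T be the true level at Visit 1 (SD τ), and let each session have independent error of SD s. Screening is S = T + e0, Visit 1 is B = T + e1, and Week 12 is Y = T + D + e2. Setting Var(D) = 100 − 2s² keeps the SD of change at the plan's 10. Both s and τ are assumptions. The MMRM contrast is approximated by an ANCOVA at Week 12.

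- Visit 1 only: V1 = Var(D) + s² + τ²s²/(τ² + s²)
- Visit 1 and screening: V2 = Var(D) + s² + τ²(s²/2)/(τ² + s²/2)

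For s = 4, τ = 15: Var(D) = 100 − 32 = 68. V1 = 68 + 16 + 225×16/241 = 98.9. V2 = 68 + 16 + 225×8/233 = 91.7. The cut is 1 − 91.7/98.9 = 7.3%.

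| s (τ = 15) | V1 | V2 | Variance cut | Power at 240/120 | Equivalent extra evaluable, 360×(V1/V2 − 1) |
|---|---|---|---|---|---|
| 2 | 99.9 | 98.0 | 1.9% | 0.895 to 0.900 | 7 |
| 3 | 99.7 | 95.4 | 4.3% | 0.896 to 0.908 | 16 |
| 4 | 98.9 | 91.7 | 7.3% | 0.898 to 0.918 | 28 |
| 5.9 | 95.3 | 81.3 | 14.7% | 0.908 to 0.945 | 62 |

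At the placebo arm's ceiling, s = 6.65, the cut would be 18%. The result depends little on τ at small s: for s = 4 it is 6.5-8% over τ = 10-20.

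**4. Bias check.** In 4,000 simulated trials per scenario (240/120, τ = 15, true effect 3.6, screening mean 1.5 points lower), the mean estimate was 3.61 with either model at s = 4 and 3.59 with either at s = 6. The standard error fell from 1.113 to 1.073 and from 1.090 to 1.006.

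**5. Relaxing the model, with a 9-day gap.** Step 3 assumes no true change between the two sessions.

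- If true change is random drift, the cut is about 3% at s = 3 and 14% at s = 5.87.
- If all true change is a fixed individual slope, then S = T − (9/84)D + e0. The cut becomes about 0% (s = 3), 2% (s = 4), 6% (s = 5) and 11% (s = 5.87).
- If subjects differ in learning with an SD of 3-5 points, the cut at s = 3 falls from 4.3% to 2.8-1.8%, and at s = 4 from 7.3% to 5.6-4.0%.

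In none of these cases does the added covariate raise the residual variance.

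**The case against.** A single pre-dose baseline is prespecified and consistent across the documents, and the screening test was planned as a check of ability. The planned power is met, so this is an optional gain. That stands.

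A reader might infer from the LEVALS SDs that one session is a poor measure of the starting level, that much of the outcome variance is session noise, or that the session SD is at least 5.9. The documents do not support this. The 2-week SDs also contain true change and differing response to treatment, and the 8.3 comes from an active arm of a 66-patient crossover study. So 5.9 is a ceiling for that arm. At τ = 15 the implied single-session reliability, τ²/(τ² + s²), is 0.98 to 0.93 for s = 2-4 and still 0.87 at 5.9. Each reading is also the best of up to 8 attempts under central assessment, with unacceptable reads set to missing.

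A shift common to all subjects goes into the intercept, but individual learning or decline does not, and it shrinks the gain (step 5).

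The change also reaches beyond the SAP model line. Protocol 8.4.3 names the Visit 1 value as the covariate. SAP 6.2.7 could make both covariates the same number. Criterion 7 rests on the investigator's judgement, so some screening reads may be missing or graded 'U' centrally. These points belong in the fix. They do not remove the gain.

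**Conclusion.** The point holds as a modest loss of efficiency. The primary analysis is valid and unbiased as written, and its power of about 90% under the plan's assumptions does not depend on this change. A plausible gain is a 2-7% cut in the Week 12 residual variance, or about 1-2 points of power, assuming a session SD of 2-4 and a between-subject SD of 15. About 15% is the upper end at a session SD of 5.9, and close to zero is possible if individual slopes persist. The size rests wholly on those assumptions, because the documents contain no reliability figure. The case for acting is that the reading is already planned and the design has little power to spare at its target effect.

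**What to change.** Before unblinding:

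- Keep change from Visit 1 as the outcome. Add screening supine SVC as a second continuous covariate beside BASE in the primary MMRM, and add it to the PROC MI VAR list for supine SVC.
- Impute a screening value that is missing or graded 'U'.
- State a rule for a missing Visit 1 value so that the same number does not enter twice. For example, with both sessions in the imputation model, impute the Visit 1 value for this endpoint in place of the 6.2.7 substitution.
- Keep the Visit 1-only model for the observed-data sensitivity analysis (SAP 6.2.5 and 7.5.4.4), so that listwise deletion removes no subject for want of a screening reading.
- List the added covariate in SAP 7.11 as a change from protocol 8.4.3.

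The cost is SAP text, one model term, one imputation variable and one degree of freedom. It needs no new visit, test or subject.
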